2.2 CLINICAL LABORATORY EVALUATION

2.2.1 *Available data*

Per protocol, the following safety laboratory parameters are expected:

- Biochemistry: creatinine, urea, phosphate, aspartate aminotransferase, alanine aminotransferase, gamma-glutamyl transpeptidase, total bilirubin, alkaline phosphatase, total cholesterol, triglycerides, sodium, potassium, calcium, chloride electrolytes.
Note: only abnormal clinically significant results will be entered in the eCRF.
- Haematology: red blood cells count, white blood cells count and differential count (absolute value and %), total haemoglobin, haematocrit, platelets count.
Note: only abnormal clinically significant results will be entered in the eCRF.
- Urinalysis: quantitative (proteins) and qualitative (proteins, ketones, microscopic examination of the sediment).
Note: only abnormal clinically significant results will be entered in the eCRF.
- Serum and urine pregnancy test and FSH.

Normal ranges are available as provided by the laboratory.

2.2.2 *Presentation of results*

All laboratory data will be listed.

2.3 VITAL SIGNS

2.3.1 *Available data*

[figure not shown]
The following vital signs parameters are collected:

- Systolic (SBP) and diastolic blood pressure (DBP) in supine position

2.3.2 *Derivation rules*

Mean values of the duplicates will be calculated per time point and rounded as detailed in section 5.3.4. Records belonging to the same duplicate will be identified using the visit and time point. In case of only one assessment available for the specific time point, its result will be considered. Throughout the analysis the mean values will be used. Individual duplicate values will only be listed.

Potential exclusion of vital signs parameters will be discussed during the review of the data by the Chiesi team. Decisions on whether values are to be excluded from the analysis will be fully documented in the DRR.

	Statistical Analysis Plan	
CLI-05993AB6-07		Final 1.0 of 22DEC2022

2.3.3 *Presentation of results*

Vital signs parameters will be summarised by means of descriptive statistics at each analysis time point by treatment. Actual values and changes from baseline will be tabulated.

All vital signs data will be listed.

2.4 ELECTROCARDIOGRAMS

2.4.1 *Available data*

The following electrocardiogram (ECG) parameters will be collected:

- Triplicate local 12-lead ECG at Screening: heart rate (HR), PR interval, QRS interval, QT interval, corrected QT interval (Fridericia) and the corresponding interpretation
- Local 12-lead single ECG: HR, PR interval, QRS interval, QT interval, corrected QT interval (Fridericia) and the corresponding interpretation

2.4.2 *Derivation rules*

For QTcF interval (ms), the following abnormality categories are defined:

- Actual values:
 - >450 ms (males) or >470 ms (females)
 - >480 ms (males)
 - >500 ms
- Changes from pre-dose:
 - Increase from pre-dose >30 ms
 - Increase from pre-dose >60 ms

Note: The worst-case, as defined in section 5.2.5, is the highest value and associated change.

Potential exclusion of ECG parameters will be discussed during the review of the data by the Chiesi team. Decisions on whether values are to be excluded from the analysis will be fully documented in the DRR.

2.4.3 *Presentation of results*

Local 12-lead single ECG parameters (HR, PR, QRS and QTcF) will be summarised by means of descriptive statistics at each analysis time point by treatment. Actual values (with their 95% CI) and changes from pre-dose (with their 90% CI) will be tabulated.

For QTcF, the number and percentage of subjects with abnormal actual values will be presented at each post-dose analysis time point and at the worst-case post-dose analysis window by treatment. In addition, the number and percentage of subjects with abnormal changes from pre-dose will be presented at each post-dose analysis window and at the worst-case analysis time point by treatment.

All local 12-lead ECG parameters will be listed. Uncorrected QT interval and the investigator's interpretation will only be listed.

	Statistical Analysis Plan	
CLI-05993AB6-07		Final 1.0 of 22DEC2022

2.5 LUNG FUNCTION

2.5.1 Available data

The following lung function (spirometry) parameters are collected: Forced Expiratory volume in 1 second (FEV₁), percent predicted FEV₁, forced vital capacity (FVC), percent predicted FVC, FEV₁/FVC ratio, percent predicted FEV₁/FVC ratio, peak expiratory flow (PEF) and forced expiratory flow 25-75%.

2.5.2 Derivation rules

Pre-dose:

The mean values of the two measurements at 45 min and 15 min will be calculated in each treatment period and rounded as detailed in section 5.3.4. In case only one assessment is available, its result will be used as pre-dose. Throughout the analysis the mean values will be used. Individual duplicate values will only be listed.

FEV₁ AUC_{0-3h} calculation:

The area under the result vs. time curve observed from time 0 up to the last measurable value (i.e., 3h) will be computed using the linear trapezoidal rule.

The change from baseline in area under the curve (AUC) normalised by time will be calculated as follows, using the trapezoidal summation rule:

- AUC normalised by time =

$$\left\{ \sum_i [(t_i - t_{i-1})(FEV1_i + FEV1_{i-1})/2] \right\} / time$$
- Change from baseline in AUC = AUC normalised by time – baseline (FEV₁₀).

where:

- for t_0 , $FEV1_0$ is the pre-dose average of t_{-45} and t_{-15} before study drug administration of each treatment period.
- t_0 is the actual time of first study drug administration,
- for $i = 5$ min, 15 min, 30 min, 1h, 1.5h and 3h, $FEV1_i$ is the actual FEV₁ value at each time point and t_i is the actual time of sample i.
- $time$ is the actual elapsed time from t_0 until t_{3h} .

Per analysis window, only the timepoint closest to the target time will be considered for AUC calculation (as per analysis windows rules reported in section 5.2.4).

	Statistical Analysis Plan	
CLI-05993AB6-07		Final 1.0 of 22DEC2022

The following rules will be applied for the AUC_{0-3h} calculation:

- In case only one pre-dose measurement is available, it will be used as pre-dose value (corresponding to time 0 for the calculation of the area under the concentration-time curve [AUC]);
- In case no pre-dose measurements are available, the entire curve will be considered missing;
- In case the last measurement for the AUC_{0-3h} (i.e. 3h) is missing, the entire curve will be considered missing;
- Single, isolated missing values (different from pre-dose or last value) will be replaced by linear interpolation using adjacent values;
- In case of two or more consecutive missing time points, the entire curve will be considered missing;
- In case of three or more missing time points, the entire curve will be considered missing.
- If the date(time) is missing or incomplete for a specific post-dose time point, then it will be imputed as the date(time) of the previous time point + the theoretical time interval between the two time points.
- If 2 or more consecutive post-dose time points have a missing or incomplete date(time), then the AUC will also be set to missing.

For FEV₁, the following abnormality categories are defined:

- Relative changes from baseline:
 - Decrease from Baseline >15 %

Potential exclusion of lung function parameters based on time window not respected will be discussed during the review of the data by the Chiesi team. Decisions on whether values are to be excluded from the analysis will be fully documented in the DRR.

2.5.3 *Inferential statistics*

Primary objective (i.e. evaluation of the potential for bronchoconstriction of each propellant):

- The relative change from baseline in FEV₁ at the 15 min post-dose time point will be analysed using an analysis of covariance (ANCOVA) model, including treatment group, subject and period as fixed effects, and FEV₁ baseline (mean of the two measurements at 45 min and 15 min pre-dose in each treatment period) as a covariate.

The adjusted mean relative change from baseline obtained with each treatment and the adjusted mean difference between HFA-152a and HFA-134a with their 95% CIs and p-values will be estimated by the model.

	Statistical Analysis Plan	
CLI-05993AB6-07		Final 1.0 of 22DEC2022

Other variables completing the evaluation of the potential for bronchoconstriction of each propellant:

- The relative changes from baseline in FEV₁ at all the other post-dose time points (5 min, 30 min, 1 h, 1 h 30 min and 3 h) will be analysed using the same model used for the relative change from baseline in FEV₁ at 15 min post-dose;
- The absolute changes from baseline in FEV₁ at all post-dose time points (5 min, 15 min, 30 min, 1 h, 1 h 30 min and 3 h) will be analysed using the same model used for the relative change from baseline in FEV₁ at 15 min post-dose.

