At each timepoint specified in [Table 1](#), subjects will perform three attempts for the measurement of FEV1 and peak expiratory flow (PEF). In order to be considered as technically satisfactory attempts, measurements should be free from cough and false-start. The highest value (in L) of FEV1 and PEF from three technically satisfactory attempts (not necessarily coming from the same curve) will be recorded. The two largest FEV1 measurements must be within 150 mL of each other (or 100 mL, if the forced vital capacity [FVC] value is  $\leq 1$  L). If the difference is larger, additional spirometry assessments (up to 8) will be made until the above criterion is met. If, at the end, the tests are not within 150 mL, the highest value of FEV1 and PEF will be recorded and used for eligibility or continuation criteria.

In case lung function measurements obtained at screening were below the expected value, (see Inclusion criterion #4 in [Section 4.2](#)), the subject will be asked to return to the investigational site once before randomisation to repeat the test. If, at that time, FEV1  $\geq 60\%$  of the predicted normal value and  $\geq 1.5$  L, the subject can be included in the study. Otherwise, the subject will be discharged and recorded as a screening failure.

If a subject shows a progressive reduction in FEV1 with each subsequent blow, with cumulative drop above 15% of the starting value, the test procedure may be terminated in the interest of the subject's safety. During the 3 h post-dose serial spirometry, the use of rescue medication should

|  |                      |
|--|----------------------|
| Clinical Study Code No.: CLI-05993AB6-07 | Version No.: 2.0     |
| EUDRACT No.: 2022-000536-36              | Date: 30 August 2022 |

be as limited as possible and rescue medication intake must be under medical control. The serial spirometries can be discontinued after the intake of rescue medication, based on the Investigator's judgement. In this case and if deemed necessary, a safety spirometry can be performed by the site. Details on intake of rescue medication during the treatment periods will be recorded in the eCRF.

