## 9. SAFETY ASSESSMENTS

The **primary objective** of this study is to compare the potential for bronchoconstriction [REDACTED] of the HFA-152a propellant *versus* [REDACTED] the HFA-134a propellant when administered alone (not in combination with other active compounds).

The potential for bronchoconstriction will be assessed through centralised spirometry assessments performed at TP1 and TP2, as described in [Section 7.3.1](#). At each treatment period, FEV1 and PEF will be assessed in pre-dose: 45 min and 15 min before T0; and in post-dose: 5 min, 15 min, 30 min, 1 h, 1 h 30 min and 3 h after T1.

The following safety variable will be considered for the evaluation of the potential for bronchoconstriction of each propellant:

- Relative change from baseline\* in FEV1 at the 15 min post-dose timepoint.

In addition, the following safety variables will be considered to complete the evaluation of the potential for bronchoconstriction of each propellant:

- Relative change from baseline\* in FEV1 at all the other post-dose timepoints (5 min and 30 min, 1 h, 1 h 30 min and 3 h after T1);
- Absolute change from baseline\* in FEV1 at all post-dose timepoints (5 min, 15 min, 30 min, 1 h, 1 h 30 min and 3 h after T1);
- Number and percentage of subjects with a relative change from baseline\* in FEV1 at each post-dose timepoint <-15%;
- Number and percentage of subjects with a relative change from baseline\* in FEV1 at any post-dose timepoint <-15%;
- Change from baseline\* in FEV1 area under the concentration-time curve from time zero to 3 hours (AUC0-3h);
- Relative change from baseline\* in PEF at all post-dose timepoints;
- Absolute change from baseline\* in PEF at all post-dose timepoints;
- Number and percentage of subjects with use of rescue medication in the 3 h after T1;
- Mean use (puffs) of rescue medication in the 3 h after T1.

\* The baseline FEV1 and PEF values are the mean of the 2 pre-dose assessments (i.e. performed 45 min and 15 min before T0).

|  |                      |
|--|----------------------|
| Clinical Study Code No.: CLI-05993AB6-07 | Version No.: 2.0     |
| EUDRACT No.: 2022-000536-36              | Date: 30 August 2022 |

The **secondary objective** of the study is to evaluate the general safety and tolerability of the two propellants.

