### 12.3.2 Missing Data

As a general rule, missing data will not be imputed.

For serial spirometry-derived parameters, the following rules will apply:

- Pre-dose FEV1 and PEF:
  - In case only one pre-dose measurement is available, it will be used as pre-dose FEV1 and PEF;
  - In case no pre-dose measurements are available, the pre-dose FEV1 and PEF will be considered missing.
- FEV1 AUC0-3h calculation:
  - In case only one pre-dose measurement is available, it will be used as pre-dose value (corresponding to time 0 for the calculation of the area under the concentration-time curve [AUC]);
  - In case no pre-dose measurements are available, the entire curve will be considered missing;
  - Single, isolated missing values (different from pre-dose) will be replaced by linear interpolation using adjacent values;
  - In case of two or more consecutive missing timepoints, the entire curve will be considered missing;
  - In case of three or more missing timepoints, the entire curve will be considered missing.

Further details on dealing with missing data, along with the handling of possible outliers, will be described in the SAP. Other critical missing data, if any, will be discussed during the review of the data. Decisions will be fully documented in the Data Review Report.

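### The FEV1 AUC0-3h summary can lose or mask subjects who needed rescue, and the plan neither counts these curves nor gives a version that keeps them

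*SAP*

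**What the plan says.** Protocol section 9 lists the change from baseline in FEV1 AUC0-3h among the variables that complete the evaluation of bronchoconstriction. SAP 2.5.4 summarises it descriptively by treatment, and Table 14.3.7.7 uses the Safety Set only.

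SAP 2.5.2 removes a whole curve in several cases. One is a missing final reading: "In case the last measurement for the AUC_{0-3h} (i.e. 3h) is missing, the entire curve will be considered missing". Another is a run of gaps: "In case of two or more consecutive missing time points, the entire curve will be considered missing". Protocol 12.3.2 has the same consecutive-gap rule and also states: "In case of three or more missing timepoints, the entire curve will be considered missing". The only repair is for a lone gap before 3 h: "Single, isolated missing values (different from pre-dose or last value) will be replaced by linear interpolation using adjacent values". SAP 5.3.1 otherwise imputes nothing.

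Protocol 7.3.1 says of rescue: "The serial spirometries can be discontinued after the intake of rescue medication, based on the Investigator's judgement". A later reading is optional: "if deemed necessary, a safety spirometry can be performed by the site". Under SAP 5.2.4, unscheduled readings are allocated to the analysis windows, and the 3 h window runs from 135 to 240 min after the last inhalation.

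Neither document has an AUC rule for readings lost, or altered, because of rescue.

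**The concern.** The deletion rules treat every gap as if it were unrelated to the outcome. A gap that follows rescue is not. The subject most likely to be rescued and stopped is one whose FEV1 fell, and the rule then discards the whole curve, including valid 5 and 15 min readings that recorded the fall.

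The study was set up because bronchoconstriction from the new propellant might be present but undetected (protocol 1.2). AUC0-3h is the only listed variable that integrates the response over the 3 h. If one propellant leads to more rescue, its AUC mean loses more reactors, the two propellants look more alike, and the two columns rest on different subjects.

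**Working it through.** **The plan's own figure.** There is none to reproduce. The documents give no expected AUC change, rescue rate or margin for this variable.

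**Step 1: apply the SAP 2.5.2 rules to each stopping point.** Post-dose readings are due at 5, 15, 30, 60, 90 and 180 min. It is assumed that at most one safety reading is taken after the stop and that it reaches the analysis data.

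| Last scheduled reading | Nothing afterwards | One safety reading in the 3 h window |
|---|---|---|
| None, 5, 15 or 30 min | Curve missing | Curve missing (60 and 90 min, at least, are consecutive gaps) |
| 60 min | Curve missing | Kept; the 90 min gap is interpolated |
| 90 min | Curve missing | Kept |

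After a stop at 30 min or earlier, a safety reading placed before the 3 h window does not help either, because the 3 h value is then missing.

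**Step 2: what one lost curve hides.** Assumptions, none of them from the documents except N:
- N = 24 (the number randomised), with the other 23 subjects at zero change.
- Profile A: a 15% fall at both 5 and 15 min.
- Profile B: a 20% fall at 5 min and a 25% fall at 15 min.
- Rescue after the 15 min reading, then the series stops.

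Formula (SAP trapezoid, in percent of baseline FEV1, time counted from the last inhalation): sum of (t_i − t_(i−1)) × (c_i + c_(i−1))/2, divided by 180.

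Pre-rescue value carried to 3 h:
- A: (5×7.5 + 175×15)/180 = 2662.5/180 = 14.79% fall. Divided by 24: 0.62 points.
- B: (5×10 + 10×22.5 + 165×25)/180 = 4400/180 = 24.44% fall. Divided by 24: 1.02 points.

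Linear return to baseline between 15 and 60 min:
- A: (5×7.5 + 10×15 + 45×7.5)/180 = 525/180 = 2.92% fall. Divided by 24: 0.12 points.
- B: (5×10 + 10×22.5 + 45×12.5)/180 = 837.5/180 = 4.65% fall. Divided by 24: 0.19 points.

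The AUC variable is an absolute change. At an assumed baseline of 3.0 L these are about 18 to 31 mL (carried) and 4 to 6 mL (recovered) per lost curve. Three lost curves in one treatment would hide 1.8 to 3.1 points or 0.4 to 0.6 points.

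**Step 3: time origin.** The SAP starts the curve at the first inhalation, up to 12 min before the last. The first interval then becomes 17 min and the divisor 192. The carried values become 2752.5/192 = 14.34% and 4520/192 = 23.54%. The recovered values become 615/192 = 3.20% and 957.5/192 = 4.99%. Divided by 24, these are 0.60, 0.98, 0.13 and 0.21 points, so the ranges hold.

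**Step 4: the series continues after rescue.** Assume −20% at 5 and 15 min, 0 at 30 min and +5% from 1 h. With the SAP origin: (17×(−10) + 10×(−20) + 15×(−10) + 30×2.5 + 120×5)/192 = 155/192 = +0.8%. A 20% fall that needed rescue then appears as a slight gain.

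**The case against.** A reader might infer that every rescued subject drops out, or that the worst responses are always removed. The documents do not support that. Stopping is at the investigator's judgement, a subject whose series continues keeps the curve, and a safety reading in the 3 h window saves curves stopped at 60 or 90 min. That part of the objection stands. It does not remove the point, because a continued series brings in post-rescue readings without adjustment.

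A reader might also set the effect against the ±10% equivalence limits. Those limits apply only to the relative change in FEV1 at 15 min. The AUC has no model, no treatment difference and no margin, so no equivalence conclusion rests on it.

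The events also remain visible elsewhere. Falls above 15% are tabulated at each time point and at worst case, rescue use and puffs are tabulated by treatment, bronchospasm has its own adverse event summary, and all readings are listed. Descriptive statistics show the non-missing n, so lost curves can be seen by treatment. These displays limit the harm, but they do not say why a curve is missing and do not correct the AUC mean.

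Finally, one might want carry-forward to replace the main derivation. That goes too far. A subject rescued before any post-dose reading would be scored as zero change, measured readings would be overwritten, and the stated rule against imputation would be set aside.

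**Conclusion.** The concern holds for a supporting descriptive variable. Under the rules as written, a subject rescued after an early fall and stopped at 30 min or earlier leaves the AUC summary. A stop at 60 or 90 min has the same result unless a safety reading falls in the 3 h window. If the series continues, bronchodilated values can offset the fall. Both routes can understate bronchoconstriction.

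The size cannot be fixed from the documents and depends mainly on what FEV1 is assumed to do after rescue. On the profiles above, the larger figure per lost curve requires the fall to persist unchanged to 3 h. With recovery by 1 h, the effect is about a fifth of that.

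A wider conclusion, that the primary result is compromised by these rules, is not supported. They act on the AUC alone, and a 15 min reading taken before rescue enters the primary ANCOVA as planned.

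**What to change.** Keep the present AUC derivation as the main row and add to Table 14.3.7.7:

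- The number of missing curves by treatment and by reason (rescue-related or other), and the number of curves that contain post-rescue readings.
- A pre-specified supplementary AUC row that keeps rescued subjects, using the last post-dose FEV1 measured before rescue for all later time points to 3 h. Subjects rescued before any post-dose reading are counted separately and not scored as zero change.

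Record this addition in SAP 6.1, which now lists no changes. Record there too the 3 h deletion rule, which is in SAP 2.5.2 but not in protocol 12.3.2.

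The cost is SAP wording and a few lines of derivation code before unblinding. Rescue times and puffs are already collected (SAP 2.6.1). The downside is one extra row that rests on single-value imputation in a few subjects. No change to the clinical rules on rescue or on stopping the series is proposed.

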2.5.4 Presentation of results

Lung function parameters will be summarised by means of descriptive statistics at each analysis time point by treatment. Actual values, absolute and relative changes from baseline (FEV₁ and PEF only) will be tabulated.

For the ANCOVA models, adjusted mean in each treatment and the adjusted mean difference between HFA-152a and HFA-134a, their 95% CIs and related p-values will be provided and tabulated from the ANCOVA. This tables will also include the type III p-values associated to model effects.

The number and percentage of subjects with FEV₁ abnormal relative changes from baseline will be presented at each post-dose time point and at the worst-case analysis visit by treatment.

The change from baseline in FEV₁ AUC_{0-3h} will be summarised by means of descriptive statistics by treatment.

All lung function parameters will be listed.

Graphs of the mean changes (both absolute and relative) from baseline over time will be prepared for FEV₁ and PEF by treatment.

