## 12. STATISTICAL METHODS

### 12.1 Sample Size

The sample size has been calculated to verify equivalence between the test treatment (HFA-152a) and the reference treatment (HFA-134a) for the relative change from baseline in FEV1 at the 15 min post-dose timepoint, with equivalence defined as a difference between the two treatments within the 10% (i.e. [-10%; +10%]).

A total of 20 evaluable subjects will ensure a 95% power to provide a 95% confidence interval (CI) of the mean difference of the relative change from baseline in FEV1 at 15 min post-dose within the above-mentioned equivalence limits (i.e. [-10%; +10%]) assuming a within-subject standard deviation (SD) of 8%.

Estimating a non-evaluable rate of 16%, a total of 24 subjects will be randomised.

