### 12.3.6 Safety Variables

Safety analyses will be based on the Safety population. For sensitivity purposes, the safety variables assessing the primary objective of the study will also be analysed in the PP population (see [Section 12.2](#)).

The safety variables of the study are presented in [Section 9](#).

The safety variable assessing the **primary objective** of the study (i.e. evaluation of the potential for bronchoconstriction of each propellant) will be analysed as follow:

- The relative change from baseline in FEV1 at the 15 min post-dose timepoint will be analysed using an analysis of covariance (ANCOVA) model, including treatment group, subject and period as fixed effects, and FEV1 baseline (mean of the two measurements at 45 min and 15 min pre-dose in each treatment period) as a covariate. The adjusted mean relative change from baseline obtained with each treatment and the adjusted mean difference between HFA-152a and HFA-134a with their 95% CIs and p-values will be estimated by the model.

The other safety variables completing the evaluation of the potential for bronchoconstriction of each propellant will be analysed as follows:

- The relative changes from baseline in FEV1 at all the other post-dose timepoints (5 min, 30 min, 1 h, 1 h 30 min and 3 h after T1) will be analysed using the same model used for the relative change from baseline in FEV1 at 15 min post-dose;
- The absolute changes from baseline in FEV1 at all post-dose timepoints (5 min, 15 min, 30 min, 1 h, 1 h 30 min and 3 h after T1) will be analysed using the same model used for the relative change from baseline in FEV1 at 15 min post-dose;
- The number and percentage of subjects with a relative change from baseline in FEV1 at each post-dose timepoint (5 min, 15 min, 30 min, 1 h, 1 h 30 min and 3 h after T1) and at any post-dose timepoint <-15% will be summarised for each treatment;
- The change from baseline in FEV1 AUC0-3h will be summarised using descriptive statistics;
- The relative and absolute changes from baseline in PEF at all post-dose timepoints (5 min, 15 min, 30 min, 1 h, 1 h 30 min and 3 h after T1) will be summarised for each treatment, using descriptive statistics;
- The number and percentage of subjects with use of rescue medication in the 3 h post-dose will be summarised for each treatment;

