1.3 EXPECTED SAMPLE SIZE

The sample size has been calculated to verify equivalence between the test treatment (HFA-152a) and the reference treatment (HFA-134a) for the relative change from baseline in FEV₁ at the 15 min post-dose time point, with equivalence defined as a difference between the two treatments within the 10% (i.e. [-10%; +10%]).

A total of 20 evaluable subjects will ensure a 95% power to provide a 95% confidence interval (CI) of the mean difference of the relative change from baseline in FEV₁ at 15 min post-dose within the above-mentioned equivalence limits (i.e. [-10%; +10%]) assuming a within-subject standard deviation (SD) of 8%.

Estimating a non-evaluable rate of 16%, a total of 24 subjects will be randomised.

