	Tabulation of the FEV ₁ relative change abnormalities as defined in section 2.5.2 at each post-dose analysis time point and at the worst-case analysis time point. Table sorted by analysis time point. Only post-dose analysis time points are shown. Template EGT008 is used, using the FEV ₁ relative change abnormalities instead.		
14.3.7.7	FEV₁: Changes from Baseline in AUC_{0-3h} (Safety Set)	SAF	TPT002
	Descriptive statistics of change from baseline in FEV ₁ AUC _{0-3h} .		

USE OF RESCUE MEDICATION

14.3.8.1	Rescue Medication Use (Safety Set)	SAF	XRT001
	Descriptive statistics of mean use of rescue medication in the first 3h post-dose by treatment and frequency tabulation of use of rescue medication.		

[REDACTED]

[REDACTED]

[REDACTED] [REDACTED]

[REDACTED]

	Statistical Analysis Plan	
CLI-05993AB6-07		Final 1.0 of 22DEC2022

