9. APPENDICES

9.1 SAS CODE

The SAS code in this section is an example and might differ from the actual code used in the statistical analysis.

Lung function ANCOVA models:

```
proc mixed;
  by param atptn;
  class trtan subjid aperiod;
  model (p) chg = trtan subjid aperiod base;
  lsmeans trtan / diff alpha= 0.05;
run;
```

Statistical Analysis Plan

CLI-05993AB6-07

Final 1.0 of 22DEC2022

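### FEV1 AUC0-3h and PEF are summarised by treatment only, so the cross-over yields no paired HFA-152a minus HFA-134a difference with a CI for either: a low-priority, cheap improvement for supportive variables

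*SAP*

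**What the plan says.** The primary objective is to compare the two propellants, in a 2x2 cross-over where each subject receives both (Protocol 2.1 and 6.5; SAP 1.1 and 1.4). Protocol section 9 makes relative FEV1 change at 15 min the main variable. It then lists others that complete the assessment of bronchoconstriction, including change in FEV1 AUC0-3h and relative and absolute change in PEF.

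The analyses fall into two tiers:

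- **Modelled.** SAP 2.5.3 fits an ANCOVA with fixed effects for treatment, subject and period and that period's FEV1 baseline as covariate. It is applied to relative and absolute FEV1 change at all six post-dose times (Tables 14.3.7.3.1 to 14.3.7.5).
- **Described only.** Under SAP 2.5.4 the AUC0-3h change "will be summarised by means of descriptive statistics by treatment". The entry for Table 14.3.7.7 in SAP 8.1 agrees: "Descriptive statistics of change from baseline in FEV", continuing with the AUC. For PEF, Protocol 12.3.6 takes "The relative and absolute changes from baseline in PEF at all post-dose timepoints" and assigns them descriptive statistics for each treatment. In the SAP, PEF results appear in descriptive Tables 14.3.7.1.x and 14.3.7.2.x and in the mean-change figures.

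SAP 5.4.1 adds a t-based CI to the descriptive statistics, but on each mean separately. SAP section 6 records no departure from the protocol.

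**The concern.** A cross-over is run so that each subject serves as their own control. A mean, SD and CI for each propellant do not use that feature. The SD in each column includes between-subject variation in response, and period is not adjusted for. The interval for the within-subject difference also depends on the correlation between a subject's two periods, which no table reports.

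AUC0-3h is the only listed variable that averages the whole post-dose curve, and PEF is the only non-FEV1 lung-function measure in the protocol's section 9 list. Both are there to complete a comparison, yet neither comes with an interval for the difference being compared. A reader left with two columns may compare their CIs as though they came from separate groups.

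**Working it through.** **The plan's own figure.** The only sample size statement concerns relative FEV1 change at 15 min: "A total of 20 evaluable subjects will ensure a 95% power" (Protocol 12.1; SAP 1.3). The inputs are a within-subject SD of 8%, limits of ±10%, a 95% CI, and a true difference of 0 (not stated; assumed).

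- SE = 8 × sqrt(2/20) = 2.53
- Power (normal approximation) = 2 × Phi(10/2.53 − 1.96) − 1 = 95.4%, which reproduces the stated 95%. The exact t-based calculation with 18 df gives 92.4%.
- 20/(1 − 0.16) = 23.8, so 24 randomised.

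None of this carries over to AUC0-3h or PEF. The documents give no SD and no margin for either, so no power can be computed for them.

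**What a paired analysis would give.** Let SDw be the variable's own within-subject SD. Before the covariate, the 95% half-width of the difference is t(0.975, n−2) × SDw × sqrt(2/n):

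- n = 20: 2.101 × sqrt(2/20) = 0.66 SDw
- n = 24: 2.074 × sqrt(2/24) = 0.60 SDw

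**What the planned columns give.** If rho is the between-period correlation of the change from baseline, each column's SD is SDw/sqrt(1 − rho). Treating the columns as independent gives a half-width of t(0.975, 2n−2) × SDw × sqrt(2/n)/sqrt(1 − rho). At n = 20 the ratio to the paired width is (2.024/2.101)/sqrt(1 − rho) = 0.963/sqrt(1 − rho).

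| Assumed rho | Independent-columns width / paired width |
|---|---|
| 0 | 0.96 |
| 0.3 | 1.15 |
| 0.5 | 1.36 |
| 0.7 | 1.76 |
| 0.8 | 2.15 |

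The documents do not give rho. Each change is measured from its own period's baseline (SAP 5.2.2), so the subject's general FEV1 or PEF level is already removed and a low rho cannot be excluded.

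**The point estimate.** With complete data in balanced sequences, subtracting the column means gives essentially the paired estimate. The columns need not hold the same subjects, however. Analysis-set membership is set per period (Protocol 12.2; SAP 5.1.1), serial spirometry may stop after rescue medication (Protocol 7.3.1), and a missing 3 h value voids that period's AUC (SAP 2.5.2). A model with subject as a fixed effect takes the contrast from subjects with data in both periods.

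**How AUC relates to what is already modelled.** SAP 2.5.2 defines the AUC change as the time-normalised AUC minus the period baseline. The trapezoid weights sum to 1, so this is a weighted sum of the six absolute FEV1 changes. At nominal times, with the clock starting at the last inhalation, the 5 and 15 min readings carry (15/2 + 25/2)/180 = 11% of the weight. SAP 2.5.2 starts the clock at first administration. If dosing takes the full 12 min allowed, the share is (27/2 + 25/2)/192 = 14%.

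**The case against.** The strongest reply is that this is a preference about supportive variables. Several parts of it stand.

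- The protocol and SAP agree, so nothing is contradicted. With no margin for AUC or PEF, an added CI has no limit to be judged against.
- FEV1 already receives paired contrasts with 95% CIs at all six times, on both scales. A consistent FEV1 difference would show there. With complete data at nominal times, the modelled AUC difference is the same weighted sum of the six absolute-change differences, so only its CI would be new.
- AUC gives about 11% to 14% of its weight to the two earliest readings, so it would dilute a brief early fall. Those times are tested individually.
- All lung-function values are listed by subject (Listing 16.2.8.4). The pairing is missing from the summaries, not lost from the data.

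What remains is that PEF has no paired contrast at all, and AUC has none with a CI.

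Two further inferences are tempting but unsupported. The SAP 9.1 code runs "by param atptn", which might suggest that PEF or AUC models are intended. That code is labelled an example, and SAP 2.5.3 and the table list restrict the models to FEV1. A reader might also carry the 8% SD over to AUC to claim a precision. That SD is for relative change at 15 min, while the AUC change is an absolute FEV1 quantity.

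**Conclusion.** The point holds as a low-priority improvement. Two variables named as completing a within-subject comparison are given no within-subject, period-adjusted difference with a CI, and the CI cannot be recovered from the planned summary tables.

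A reader might go further and infer that the equivalence conclusion is weakened or that the SAP is in error. The documents do not support either. The primary analysis and the other FEV1 time points are paired and period-adjusted, and the SAP follows the protocol.

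The size cannot be fixed from the documents. The width ratio runs from 0.96 (no loss) at rho = 0 to 1.36 at 0.5 and 1.76 at 0.7. It depends on an assumed rho, and on a reader treating the columns as independent, which the plan does not propose. Redacted parts cannot be checked, but the lung-function sections and table entries relied on here are readable.

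**What to change.** In SAP 2.5.3, extend the existing ANCOVA to:

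- change from baseline in FEV1 AUC0-3h, with the period's FEV1 baseline as covariate;
- relative and absolute change in PEF at each post-dose time, with the period's PEF baseline as covariate.

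Report the adjusted HFA-152a minus HFA-134a difference with its 95% CI in Table 14.3.7.7 and in PEF counterparts of Tables 14.3.7.3.1 to 14.3.7.5. Label the results supportive, with no equivalence or multiplicity claim.

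The cost is SAP wording and a few outputs from the existing model; no new data are needed. The downside is up to 13 more unadjusted contrasts (1 for AUC, plus 2 scales × 6 times for PEF) on top of the present 12 for FEV1. SAP 2.5.4 attaches p-values to every ANCOVA, so add a sentence that these are shown as estimates and CIs without p-values.
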